1.3 Unblinding

Treatment assignments are known only to the responsible unblinded vaccine administrators at the trial center. Personnel at the clinical study site including, investigators and study staff, immunology laboratory, and study subjects will remain blinded to individual subject treatment assignments until after the database lock for the final analysis unless emergency unblinding is necessary.

All treatment assignments, vaccine storage and accountability, and/or dosing-related matters will be monitored by a designated "unblinded monitor." Any deviations will be discussed, documented, and resolved by the unblinded monitor and the unblinded site personnel. Reports provided by the unblinded monitor will be reviewed by designated unblinded personnel at either Novavax or the clinical research organization (CRO), not involved with the main trial team. No reports from the unblinded monitor will be released to the Trial Master File (TMF) until database lock for Day 364.

1.4 Scope of the Analysis Plan

This statistical analysis plan (SAP) provides a detailed outline of the safety and immunogenicity analyses in accordance with Study Protocol qNIV-E-301Version 4.0, dated 31 October 2019, and will address the analysis presentation of the unblinded data as well as the final review of all data for the completed study.

An unblinded data review will be conducted upon completion of all Day 28 visits, which will include all primary endpoints (HAI antibody responses assayed with egg-propagated virus) testing of associated Day 28 serum samples for all 4 vaccine homologous influenza strains (ie, 2 influenza A and 2 influenza B strains) and safety data through Day 28. Data concerning secondary and exploratory endpoints will be included in the unblinded review of Days 0 and 28 as they become available.

Day 364 final analysis will be conducted when all immunogenicity and safety data through Day 364 have been entered, reviewed, and all queries related to the data have been addressed. Immunogenicity data required prior to the Day 364 analysis will include the mandated timepoints (Days 0 and 28) for the primary and secondary endpoints, with the latter including the four vaccine-homologous A and B strain(s) and at least one antigenically-drifted influenza strain for HAI antibody titers assayed with both egg-propagated virus and wild-type VLP reagents. Immunogenicity data required prior to the Day 364 analysis will also include HAI antibody response at additional time-point Day 182 tested with a subset of subjects pursuant to secondary endpoints. Testing of additional antigenically-drifted influenza strain responses by HAI, and also Microneutralization (MN) and cellular response testing pursuant to the exploratory objectives may be completed later and included in addenda to the study report.

2 OBJECTIVES AND ENDPOINTS

2.1 Study Objectives

2.1.1 Primary Objectives

- To demonstrate the non-inferior immunogenicity of 240 μg Quad-NIV co-formulated with 75 μg Matrix-M1 adjuvant, relative to a US-licensed comparator, Fluzone Quadrivalent, in clinically stable adults \geq 65 years of age, in terms of hemagglutination inhibition (HAI) (assayed with egg-propagated virus) antibody responses to all Quad-NIV homologous influenza strains (ie, 2 influenza A and 2 influenza B strains) at Day 28 post-vaccination.
- To describe the safety profile of 240 µg Quad-NIV co-formulated with 75 µg Matrix-M1 adjuvant, and the comparator in clinically stable adults ≥ 65 years of age. The safety profile will include solicited short-term reactogenicity; 28-day all adverse event (AE) profile; 1-year post-injection medically-attended adverse event (MAE), serious adverse event (SAE), and significant new medical condition (SNMC), including immunologically-mediated adverse events of special interest (AESIs).

2.1.2 Secondary Objectives

• To describe the immunogenicity of 240 μg Quad-NIV co-formulated with 75 μg Matrix-M1 adjuvant, and of a US-licensed comparator, Fluzone Quadrivalent, in clinically stable adults ≥ 65 years of age, in terms of HAI (assayed with both egg-propagated virus and wild-type VLP reagents) antibody responses to all Quad-NIV homologous influenza strains (2 influenza A and 2 influenza B strains) and at least 1 antigenically drifted A or B strain in terms of geometric mean titers (GMTs), geometric mean ratio (GMR), seroconversion rate (SCR), seroprotection rate (SPR), and the baseline adjusted ratio of GMTs between treatment arms at Day 28. An additional time-point at Day 182 may be tested by HAI for these outcomes in a subset of subjects in each treatment group.

2.1.3 Exploratory Objectives

- To evaluate the superior immunogenicity of 240 μg Quad-NIV co-formulated with 75 μg Matrix-M1 adjuvant, relative to Fluzone Quadrivalent, in clinically stable adults \geq 65 years of age, in terms of HAI (assayed with both egg-propagated virus and wild-type VLP reagents) antibody responses against all 4 vaccine homologous influenza strains (ie, 2 influenza A and 2 influenza B strains) and 1 2 antigenically-drifted A and/or B strains at Days 0 and 28 post-vaccination.
- To describe the immunogenicity of 240 μg Quad-NIV co-formulated with 75 μg Matrix-M1 adjuvant, and of a US-licensed comparator, Fluzone Quadrivalent, in clinically stable adults ≥ 65 years of age, in terms of microneutralization (MN) responses to vaccine-homologous and/or antigenically-drifted influenza strains at Days 0 and 28 post-vaccination, in terms of GMTs, GMR, SCR, and the baseline adjusted ratio of GMTs between treatment arms at Days 28 post-vaccination. *Note: Due to the time-consuming nature of MN testing, this exploratory objective may be completed in a subset of participants in each study treatment group and/or a subset of strains after the initial study HAI data are*

complete and reported in an addendum. Laboratory staff will remain blinded as to treatment assignments until all projected MN tests are complete. Similarly, an additional time-point at Day 182 may also be tested.

• To describe the quality and amplitude of cell-mediated immune (CMI) responses in healthy adults ≥ 65 years of age to vaccination with 240 μg Quad-NIV co-formulated with 75 μg Matrix-M1 adjuvant, as measured by functional T cell responses based on intracellular cytokine analysis. Additional markers of CMI (eg, memory B cells and/or other T cell subsets) may be evaluated depending on availability/recovery of cell volume. Due to the laborious nature of the cellular assays, they will be performed on subjects from a limited number of participating sites and results may be reported as an addendum to the main clinical study report.

2.2 Study Endpoints

2.2.1 Primary Endpoints

• Comparative HAI antibody responses (assayed with egg-propagated virus) on Day 28, summarized in terms of the ratio of geometric mean titers (GMTs) AND seroconversion rate (SCR) difference, between subjects receiving Quad-NIV or Fluzone Quadrivalent for all 4 vaccine homologous influenza strains (ie, 2 influenza A and 2 influenza B strains).

Non-inferiority for each homologous strain will be demonstrated if:

○ The lower bound of the two-sided 95% CI on the ratio of the GMTs $(GMT_{OuadNIV}/GMT_{Fluzone})$ is ≥ 0.67 ,

AND

- The lower bound of the two-sided 95% CI on the difference between the SCRs ($SCR_{QuadNIV}$ - $SCR_{Fluzone}$) is \geq -10%.
- Number and percentage (95% CI) of subjects with solicited local and systemic adverse events over the 7 days post-injection (ie, Day 0 through Day 6, inclusive); all adverse events through 28 days post-injection (ie, Day 0 through Day 27, inclusive); and MAEs, SAEs, and SNMCs including AESIs through 1 year post-injection.

2.2.2 Secondary Endpoints

- HAI antibody titers (assayed with both egg-propagated virus and wild-type VLP reagents) at Days 0 and 28 specific for vaccine-homologous A and B strain(s), and antigenically-drifted influenza strains. An additional time-point at Day 182 may also be tested with a subset of subjects. Derived/calculated endpoints based on these data will include:
 - o GMT defined as the antilog of the mean of the log-transformed HAI titers, on Days 0 and 28.
 - o Geometric mean ratio (GMR) defined as the ratio of post-vaccination to pre-vaccination (Day 0) HAI GMTs (GMR_{Post/Pre}) on Day 28.

- Seroconversion rate (SCR) defined as proportion of subjects in a given treatment group with either a baseline reciprocal (Day 0) titer of < 10 and a post-vaccination reciprocal titer ≥ 40, or a baseline reciprocal (Day 0) titer of ≥ 10 and a post-vaccination titer ≥ 4-fold higher on Day 28.

- Seroprotection rate (SPR) defined as the proportion of subjects with a reciprocal HAI titer ≥ 40 on Day 28.
- o Ratio of GMTs between treatment arms at Day 28 post-vaccination (adjusted for intergroup variation in baseline [pre-vaccination] titers).

2.2.3 Exploratory Endpoints

• Comparative HAI antibody responses (assayed with both egg-propagated virus and wild-type VLP reagents) on Day 28, summarized in terms of the ratio of geometric mean titers (GMTs) AND seroconversion rate (SCR) difference, between subjects receiving Quad-NIV or Fluzone Quadrivalent for all 4 vaccine homologous influenza strains (ie, 2 influenza A and 2 influenza B strains) and 1 - 2 antigenically-drifted A and/or B strains.

Superior immunogenicity for each strain will be demonstrated if:

 \circ The lower bound of the two-sided 95% CI on the ratio of the GMTs (GMT_{QuadNIV}/GMT_{Fluzone}) is greater than 1.5,

AND

- The lower bound of the two-sided 95% CI on the difference between the seroconversion rates (SCR_{QuadNIV}-SCR_{Fluzone}) is greater than 10%.
- Microneutralization (MN) responses: Neutralizing antibody titers specific to vaccine-homologous A and B strain(s) and/or antigenically-drifted influenza strains, at Days 0 and 28 post-vaccination, as measured by a microneutralization assay. An additional time-point at Day 182 may also be tested. Derived/calculated endpoints based on these data will include:
 - o GMT defined as the antilog of the mean of the log-transformed neutralizing titer for a given treatment group.
 - o GMR defined as the ratio of post-vaccination and pre-vaccination neutralizing GMTs within the same treatment group (designated as GMR_{Post/Pre}).
 - o SCR defined as proportion of subjects in a given treatment group with either a baseline reciprocal titer of < lower limit of quantitation (LLOQ) and a post-vaccination reciprocal titer 4-fold higher than the LLOQ, or a baseline reciprocal titer of ≥ LLOQ and a post-vaccination reciprocal titer ≥ 4-fold higher than the baseline titer.
 - o Ratio of GMTs between treatment arms at Day 28 post-vaccination (adjusted for intergroup variation in baseline [pre-vaccination] titers).
- Counts and/or proportions of Days 0, 7, 28, and 182 peripheral blood effector memory T cell populations that secrete one or more of IL-2, CD40L, IFN-γ, and TNF-α cytokines

following *in vitro* restimulation with HA in subjects selected for cellular immune response monitoring. Counts and/or proportions of additional markers of CMI, as appropriate.

3 ANALYSIS POPULATIONS

The following subject populations will be used in all analyses:

3.1 Safety Population

The Safety Population includes all trial subjects that provide consent, are randomized, and receive the test article. The Safety Population will be used for all safety analyses; and will be analyzed as actually treated.

3.2 Per-Protocol Population

The Per-Protocol (PP) Population includes all subjects in the Safety Population that receive the assigned dose of the test article according to protocol, have HAI serology results for Day 0 and Day 28, and have no major protocol deviations affecting the primary immunogenicity outcomes as determined by Novavax prior to database lock and unblinding. The PP Population will be the primary population used for immunogenicity analyses.

3.3 Intent-to-Treat Population

The Intent-to-Treat (ITT) Population includes all subjects in the Safety Population that provide any HAI serology data. The ITT Population will be the secondary population used for any immunogenicity analyses and will be analyzed according to treatment as randomized. Analysis using the ITT population will not be performed if it differs from the PP population by $\leq 5\%$ of the subjects for each of the 2 treatment groups.

3.4 Discussion of Populations to be Used for Various Analyses

Subject demographic, baseline data, and safety AE summaries will be based on the Safety Population. All subjects enrolled (randomized) will be used for subject disposition. Immunogenicity summaries and associated statistical analyses will be based primarily on the PP Population and secondarily on the ITT Population.

3.4.1 Protocol Deviations

A protocol deviation (PD) will be defined as a failure to comply with the requirements set forth in the protocol. PDs may be determined programmatically through the course of the trial. Examples of programmatically-determined PDs are provided in Table 2.

Table 2: Programmatically-Determined Protocol Deviations

Missed Visit
Out of Window Visit
Trial Procedure Not Done
Randomization Error

The following rules will be applied to capture programmatically determined PDs.

- Missed Visit information in protocol deviations derived from the eCRF will be subordinate to those programmatically-determined missed visits and will not be used for the formal CSR. Missed Visit status will not be triggered by the "Subject Diary Review" procedure. Missed Visit applies to planned in-clinic visits at Days 0, 7, 28, and 182. Telephone contacts will not be counted as missed visits, though the presence or absence of these visits will be apparent in the data listings. If a subject withdraws from the study early, no subsequent protocol deviations will be checked.
- Out of Window Visit will be determined by comparing the actual visit day to the scheduled visit day. If a subject missed a particular visit (s), (s)he will not be considered as "Out of Window" for that visit but will be counted as "Missed Visit". Out of Window visit applies to all planned trial visits at Days 0, 3, 7, 28, 90, 182, and 364. Telephone contacts will not be reviewed for visit windows, however the date of occurrence will be present in the data listings.
- Trial Procedure Not Done will include trial procedures ("Physical Exam", "Vital Signs", "Serology", "PBMC for CMI" and "Trial Treatment Injection") listed in Appendix 1 "Trial Procedure Schedule" in the protocol. If a subject had "Missed Visit" or "Out of Window Visit", (s)he will not be counted as "Procedure Not Done" again for the intended visit.
- Randomization Error will be determined programmatically by seeking possible erroneous scenarios including mis-stratification based on erroneous age or 2018-19 influenza vaccine history, possible multiple randomization, randomization without treatment, or treatment without randomization.

Additionally, all protocol deviations identified by site personnel prior to a monitoring visit or by the Site Monitor (Clinical Research Associate (CRA)) during on-site or remote visits and/or during site management activities will be documented in the 'Protocol Deviation' section of EDC by the Site personnel responsible at the site. Deviations entered into EDC by the site will be reviewed by the Site Monitor responsible for the site. The PD listing suitable for import for SAS will provide the category of protocol deviation and the corresponding description of each protocol deviation, with a flag to indicate if a deviation was considered major and resulted in the exclusion of the subject from the PP analysis set.

3.4.1.1 Major Protocol Deviations Assessment

Prior to unblinding, the medical and operational leads will jointly assess protocol deviations and create a consensus final protocol deviations assessment file. Protocol deviations deemed to indicate clear violations of GCP and/or subject consent; or to have a likely effect on the primary immunogenicity outcomes will exclude those subjects from the PP analysis set. In general, the following will be deemed "major" deviations:

- Failure to obtain completely executed and documented informed consent.
- Failure to receive, or document receipt of, the study treatment as randomized.

- For inclusion in the PP Population, failure to provide or to provide out of protocol-specified window, a sample for serologic analysis on Day 0 and on Day 28.
- Receipt of immunosuppressive medication from Day 0 until the Day 28 visit.
- Receipt of any non-protocol influenza vaccine between 6 months prior to Day 0 and through the Day 28 visit.
- Other deviations deemed likely by the Sponsor to degrade the immune response to the test article, including especially (but not limited to):
 - o receipt of non-study vaccines in the 28 days preceding and 14 days following study test article, or
 - o receipt of any immune globulin preparation in the 3 months before or 28 days following study test article.

4 SUBJECT DISPOSITION

The number of subjects consented, randomized, and vaccinated will be presented by treatment group for all subjects.

The number (percentage) of subjects in the Safety Population, PP Population, and ITT Population who have completed the study through Day 28 and through Day 364 will be summarized by treatment group.

The number (percentage) of subjects who discontinue the study prior to Day 364 and the reason for discontinuation (eg, adverse event, investigator decision, lost to follow-up, non-compliance, etc.) will be presented by treatment group. A listing of all subjects in the Safety Population who are discontinued will be presented by treatment group, reason for discontinuation, and day of last study contact. Day of last study contact will be calculated as follows: date of study discontinuation (as recorded on EOS eCRF) minus date of Day 0 vaccination.

The number (percentage) of subjects in the Safety Population with Major Protocol Deviations will be summarized by treatment group. A listing of all subjects in the Safety Population with one or more protocol deviations recorded through Day 28 and through Day 364, will be provided and will include: treatment group, study day associated with the deviation, protocol deviation category, and a description of the deviation as recorded by the site.

5 DEMOGRAPHICS AND OTHER BASELINE CHARACTERISTICS

Demographic parameters and other baseline characteristics (age at Day 0 vaccination, gender, ethnicity, race, height [cm], weight [kg], as well as history of receipt of 2018-19 influenza vaccine will be summarized by each treatment group for all subjects in the Safety Population and ITT Population.

Descriptive statistics (total number of subjects [n], mean and standard deviation, median, minimum and maximum values) will be summarized for weight (kg) and height (cm) measurements recorded at Study Day 0. Age (years) at the Day 0 vaccination will be calculated

as the closest lower integer result of (Date of Study Day 0 – Date of Birth) / 365.25, and will be summarized using the above descriptive statistics.

The number and percentage of subjects for Gender (eg, "Male", "Female"), Ethnicity (ie, Hispanic or Latino, not Hispanic or Latino), Race (ie, American Indian or Alaska Native, Asian, Black or African American, Native Hawaiian or Other Pacific Islander, and White) will be summarized.

Medical history and physical examination diagnoses/abnormalities will be coded using MedDRA version 22.0. Baseline medical history and physical examination findings recorded on Day 0 (prior to vaccination) will be summarized separately, by MedDRA system organ class (SOC), preferred term (PT), and treatment group for all subjects in the Safety Population. Within each SOC and PT, the number and percentage of subjects with at least one abnormality will be presented, respectively. Multiple abnormalities within a given SOC and PT for a subject will be counted once.

6 EXTENT OF EXPOSURE

6.1 Study Vaccine

Subject vaccination exposure will be summarized as the number and percentage of subjects who received test article at Day 0 by treatment group.

6.2 Concomitant Medication

The assessment of concomitant medication use by the subject during the study will coincide with the collection period of adverse events. Concomitant medications recorded on the Concomitant Medications CRF will be summarized by WHO-DRUG Anatomical Therapeutic Chemical (ATC) Term and standardized (generic) medication name based on WHODD GLOBAL B3-Mar2019. The number (percentage) of subjects who record one or more concomitant medications will be presented by treatment group for all subjects in the Safety Population. Multiple occurrences of medication usage for a subject will be counted only once within an ATC term and standardized medication name. The presentation of concomitant medications will include all medications recorded on the Concomitant Medications CRF, including medications with a missing or partial start date or a start date prior to Study Day 0 vaccination. A separate listing of treatment-emergent new concomitant medications will be presented.

7 ANALYSES ADDRESSING PROTOCOL OBJECTIVES

7.1.1 Analyses of Primary Immunogenicity Objectives

The Per-Protocol (PP) population (ie, randomized subjects who received the assigned dose of the test article according to the protocol, have HAI serology results at Day 0 and Day 28, and have no major protocol deviations) will be the primary population for immunogenicity analysis. A separate intent-to-treat (ITT) population analysis will not be produced unless > 5% of at least 1 treatment group is excluded from the PP population. No missing data will be imputed. For

Version 3.0 - 01 November 2019

GMTs and GMRs, titers reported below the lower limit of quantitation (LLOQ, ie, below the starting dilution of assay reported as "< 10") will be set to half that limit (ie, 10/2 = 5).

For purposes of determining non-inferiority (and exploratory superiority) in immunogenicity of 240 µg Quad-NIV co-formulated with 75 µg Matrix-M1 adjuvant, relative to a US-licensed comparator, Fluzone Quadrivalent, for all Quad-NIV homologous influenza strains (2 influenza A and 2 influenza B strains) at 28 days post-vaccination, derived/calculated endpoints will include:

- Two-sided 95% CIs for the ratio of Day 28 post-vaccination GMTs between Quad-NIV and Fluzone Quadrivalent will be constructed using log normal distribution. The log₁₀ values will be used to construct a CI using the analysis of covariance (ANCOVA) with treatment group and baseline at Day 0 (adjusted for intergroup variation in baseline [pre-vaccination] titers) as the covariates under two-sided type I error rate of 0.05. No type I error rate adjustments will be made. The mean difference and the corresponding CI limits will then be exponentiated to obtain the ratio of GMT and the corresponding CI.
 - A sample SAS code for between-group geometric mean ratio (GMR_{new/ref}) is given below:

```
proc mixed data= fludata;
      by Visit;
      class Treatment;
      model log(HAI 28) = log(HAI D0) Treatment/noint;
      lsmeans Treatment/cl diff e alpha=0.05;
run;
```

- Two-sided 95% CIs for the difference of the SCRs between Quad-NIV and Fluzone Quadrivalent will be based on the Newcombe hybrid score (METHOD = SCORE riskdiff-option for PROC FREQ in SAS).
 - Pearson Chi-Square p-value will be derived for testing the equality of SCRs between two groups; otherwise Chi-Square p-value will be derived with continuity adjustment if small sample size. The Newcombe method will be used to construct its 95% confidence interval with the following sample SAS code:

```
proc freq data = fludata noprint;
      tables trt*seroconvind / riskdiff (column=2 cl=(newcombe))
      chisq;
run;
```

7.2 **Analysis of Secondary and Exploratory Immunogenicity Objectives**

Immunogenicity of 240 µg Quad-NIV co-formulated with 75 µg Matrix-M1 adjuvant, relative to a US-licensed comparator, Fluzone Quadrivalent, based on HAIs (assayed with both egg-propagated virus and wild-type VLP reagents) for all vaccine-homologous influenza A and B strains, and at least 1 antigenically-drifted A or B strain at Day 28 post-vaccination, will be measured in terms of:

- Geometric mean titer (GMT) defined as the antilog of the mean of the log-transformed HAI titers, on Days 0 and 28.
- Geometric mean ratio (GMR) defined as the ratio of post-vaccination to pre-vaccination (Day 0) HAI GMTs (GMR_{Post/Pre}) on Day 28.
 - Within-group geometric mean ratio (GMR_{post/pre}) for each arm will be conducted using paired t distribution. A sample SAS code is given below:

```
proc ttest data= fludata alpha=0.05;
      by Treatment Visit;
      PAIRED log(HAI D28) *log(HAI D0);
run;
```

- Seroconversion rate (SCR) defined as proportion of subjects in a given treatment group with either a baseline reciprocal (Day 0) titer of < 10 and a post-vaccination reciprocal titer \geq 40, or a baseline reciprocal (Day 0) titer of \geq 10 and a post-vaccination titer \geq 4-fold higher on Day 28.
 - SCR and corresponding 2-sided exact binomial 95% CIs will be calculated using the Clopper-Pearson method with the following sample SAS code:

```
proc freq data=fludata noprint;
      by Treatment;
      tables seroconvind / binomial(exact) alpha=.05;
      output out=out1 binomial;
run;
```

- Seroprotection rate (SPR) defined as the proportion of subjects with a reciprocal HAI titer \geq 40 on Day 28.
 - SPR and corresponding 2-sided exact binomial 95% CIs will be constructed similarly using the Clopper-Pearson method. Chi-Square p-value will be derived for testing the equality of SPRs between two groups similarly as SCR described above. The Newcombe method will be used to construct its 95% confidence interval.
- Ratio of GMTs between treatment arms at Day 28 post-vaccination (adjusted for intergroup variation in baseline [pre-vaccination] titers).

An additional time-point at Day 182 may also be tested.

Microneutralization (MN) responses at Days 0 and 28 post-vaccination will include:

- GMT defined as the antilog of the mean of the log-transformed neutralizing titer for a given treatment group.
- GMR defined as the ratio of post-vaccination and pre-vaccination neutralizing GMTs within the same treatment group (designated as GMR_{Post/Pre}).
- SCR defined as proportion of subjects in a given treatment group with either a baseline reciprocal titer of < lower limit of quantitation (LLOQ) and a post-vaccination reciprocal

titer 4-fold higher than the LLOQ, or a baseline reciprocal titer of \geq LLOQ and a post-vaccination reciprocal titer \geq 4-fold higher than the baseline titer.

• Ratio of GMTs between treatment arms at Day 28 post-vaccination (adjusted for intergroup variation in baseline [pre-vaccination] titers).

An additional time-point at Day 182 may also be tested.

The methods for the calculation of GMT, GMR, SCR, and ratios of GMTs for Microneutralization (MN) responses are the same as those for HAI responses.

Analysis of exploratory CMI response endpoints will be performed on a subset of approximately 140 subjects from several pre-designated clinical sites (approximately 70 subjects per treatment arm) and results may be reported as an addendum to the main clinical study report.

The analysis for CMI response may include:

- Counts of Peripheral Blood T Cells characterized based on various cell surface markers at Day 0, 7, 28, and 182.
- Counts and proportion of specific CD4 T cells expressing two and three cytokines in response to influenza hemagglutinin stimulation at Day 0, 7, 28, and 182.
 - The boxplots for counts of two and/or three cytokines may be generated based on log₁₀ scale values.
- GMR ratio of geometric mean of specific CD4 T cells expressing two/three cytokines between Treatment A (Quad-NIV) and Treatment B (Fluzone) at Day 7, 28, and 182.
 - The log₁₀ values will be used to construct a 90% CI using the analysis of covariance (ANCOVA) with treatment group and baseline at Day 0 as the covariates under two-sided type I error rate of 0.10.
 - LLOQ is defined as 1. If counts is zero, it will be set to half that limit to take log_{10} scale (ie, $log_{10}(1/2) = -0.3$).
- Geometric mean ratio of specific CD4 T cells expressing two/three cytokines between Day 7/28/182 and Day 0.
 - LLOQ is defined as 1. If counts is zero, it will be set to half that limit to take log_{10} scale (ie, $log_{10}(1/2) = -0.3$).
 - The bar graphs with corresponding CIs may be generated.
- Reverse cumulative distribution displays of double- or triple-staining cell counts for homologous influenza strains (ie, 2 influenza A and 2 influenza B strains) at Day 7/28/182 post-vaccination may be displayed separately by the treatment group.

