9 SAMPLE SIZE CONSIDERATIONS

This study has a single comparison between Quad-NIV and Fluzone Quadrivalent at Day 28 post-vaccination for the primary immunogenicity objective. No adjustment of the Type I error rate for multiple comparisons is warranted since the simultaneous successes of all 8 comparisons planned for the 4 strains contained in the vaccines and the two endpoints (GMT and SCR) are required for the demonstration of the primary non-inferiority objective of the study.

Non-inferiority is defined as the lower bound of the 2-sided 95% CI on the ratio of GMTs (Quad-NIV vs Fluzone) ≥ 0.67 (ie, unadjusted 1-sided p-value < 0.025 against the null hypothesis of H0: Ratio of GMT < 0.67) and the lower bound of the two-sided 95% CI on the

difference of the SCRs (Quad-NIV - Fluzone) \geq -10% (ie, unadjusted 1-sided p-value < 0.025 against the null hypothesis of H0: Difference of SCRs < -10%).

For the calculation of sample size estimation, we used assumptions of true differences, ie, the ratio of GMTs (Quad-NIV vs Fluzone Quadrivalent) is 1.0 for all 4 homologous strains, and the difference of the SCRs is -2% for each of the 4 homologous strains, based on the average performance in the previous trial (qNIV-E-201). To achieve an overall 90% power (ie, ~ 97.5% power for each of the 4 strains) to demonstrate a non-inferiority margin for SCR difference of -10%, the SCR of reference group (Fluzone Quadrivalent) is assumed to be 0.5 and the SCR of treatment group (Quad-NIV) is assumed to be 0.48 under the null hypothesis of inferiority (H0: Difference of SCRs < -10%). The significance level of the testing is 0.025. Sample size was estimated to be 1195 in each group by assuming equal size in each group. The sample size accounted for a 10% attrition rate for the per-protocol population such that the primary analysis population for all immunogenicity endpoints will be 1325 in each group.

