12.2 Adjustments for Covariates

Comparison of GMTs between treatment groups will be adjusted for pre-vaccination titer.

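### Cheap improvement, not an error: the SCR difference, which alone limits power, is compared without adjustment for the Day 0 titer that the GMT ratio is already adjusted for

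*SAP*

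**What the plan says.** SAP 7.1.1 and Protocol 10.4.1.1 give the same method for the seroconversion comparison: "Two-sided 95% CIs for the difference of the SCRs between Quad-NIV and Fluzone Quadrivalent will be based on the Newcombe hybrid score". The sample SAS code in SAP 7.1.1 is a PROC FREQ table of treatment by seroconversion status, with no covariate and no stratum.

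For the GMT ratio the same sections specify ANCOVA on log10 titer with the Day 0 value as covariate. SAP 12.2 confines adjustment to that endpoint: "Comparison of GMTs between treatment groups will be adjusted for pre-vaccination titer".

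SAP 7.2 defines seroconversion from the Day 0 titer. A subject below 10 at baseline needs at least 40 after vaccination; a subject at 10 or above needs at least a four-fold rise.

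SAP 9 requires all eight comparisons (four strains, two endpoints) to succeed. It states 100% power for the GMT criterion and sizes the trial on SCR: "To achieve an overall 90% power (ie, ~ 97.5% power for each of the 4 strains").

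**The concern.** The adjustment is placed where it can hardly help. The GMT comparisons have power to spare, while the four SCR comparisons carry nearly all the risk of missing a true non-inferiority result, and the design already assumes a true deficit of 2 points.

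The Day 0 titer is a natural predictor of seroconversion, since the endpoint is a rise from that titer and its rule changes at 10. Under SAP 3.2 every per-protocol subject has a Day 0 HAI result, so adjusting would need no new data and lose no one. If the titer does predict seroconversion, a standardised risk difference would be narrower at the same sample size, for the same estimand and margin. At stake is some avoidable chance of a false failure on at least one strain.

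**Working it through.** **Inputs from SAP 9.** "The significance level of the testing is 0.025" (one-sided). The aim is "to demonstrate a non-inferiority margin for SCR difference of -10" percent. The assumed truth is that "the difference of the SCRs is -2% for each of the 4 homologous strains"; "the SCR of reference group (Fluzone Quadrivalent) is assumed to be 0.5" and the "treatment group (Quad-NIV) is assumed to be 0.48". Evaluable n is 1195 per group. The SD of log10 HAI titer is 0.3 to 0.4.

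**1. Reproduce the sample size.** The variance term is 0.50×0.50 + 0.48×0.52 = 0.4996. The distance from truth to margin is 0.10 − 0.02 = 0.08. For 97.5% power, n = (1.96 + 1.96)² × 0.4996 / 0.08² ≈ 1200 per group. The approximate Farrington–Manning form gives 1194. The stated 1195 is reproduced.

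**2. Which endpoint limits power.**
- SCR: SE = √(0.4996/1195) = 0.02045. Power = Φ(0.08/0.02045 − 1.96) = 97.46% per strain. For four independent strains, 0.9746⁴ = 90.2%. Simulated Newcombe power is also 97.46% per strain.
- GMT: −log10(0.67) = 0.174. At SD 0.4, SE = 0.4×√(2/1195) = 0.0164, so power = Φ(0.174/0.0164 − 1.96), which is effectively 100%. It is still above 99.99% at SD 0.6.

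**3. Effect of adjustment.** Let R2 be the share of the variance in seroconversion explained by the Day 0 titer. The documents do not give it, so it is an assumption. To a good approximation SE = √[0.4996 × (1 − R2)/1195].

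| Assumed R2 | Power per strain | Four strains, independent | 95% CI half-width (points) | n per group for 97.5% |
|---|---|---|---|---|
| 0 (crude) | 97.5% | 90.2% | 4.01 | 1200 |
| 0.02 | 97.7% | 91.1% | 3.97 | 1176 |
| 0.05 | 98.0% | 92.3% | 3.91 | 1140 |
| 0.10 | 98.5% | 94.1% | 3.80 | 1080 |
| 0.17 | 99.0% | 96.1% | 3.65 | 996 |

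**4. Where the R2 range comes from.** The proposed model was simulated with an SCR of 50%, baseline log10 mean 1.0–1.6 and SD 0.3–0.4, log10 fold-rise SD 0.4, and correlation of baseline with log fold rise of −0.1 to −0.5. R2 ran from 0.015 to 0.17. All these inputs are assumed; the plan's SDs of 0.3–0.4 are not labelled as baseline SDs. At a baseline mean of 1.0, a stronger negative correlation gave less gain, so the result is sensitive to them. A wider set (baseline mean 1.4, SD 0.3–0.5, Day 28 SD 0.3–0.4, Day 0 to Day 28 correlation 0.3–0.7) gave 0.00–0.29 for a linear titer term alone.

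**5. Correlated strains.** The four results come from the same subjects. With an assumed correlation of 0.3–0.5 between the test statistics, crude four-strain power is already about 91.0–92.0%. The gain at R2 = 0.05 then falls from about 2 points to about 1.6–1.8.

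**6. Type I error.** At a true difference of −10 points, the crude Newcombe rule passes in 2.6% of simulated trials. In paired simulations of a crude (Wald) and an adjusted interval (8000 trials each, Monte Carlo SE about 0.2 points), the rates were 2.5% and 2.4% at R2 near 0.05, and 2.2% and 2.6% at R2 near 0.10.

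**7. Chance baseline imbalance.** Its 95% contribution to the crude difference is ±1.96 × √(R2 × 0.4996/1195). That is ±0.9, ±1.3 and ±1.8 points for R2 of 0.05, 0.10 and 0.20. It is part of the crude variance, so the crude interval already covers it on average.

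**The case against.** The best case for the plan is that nothing in it is wrong. The crude Newcombe interval is prespecified, is the same in protocol and SAP, matches the crude proportions used to size the study, and delivers the stated 90%. All of that stands.

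Three stronger readings are tempting, and the documents support none of them.
- A reader might infer that the plan ignores the Day 0 titer for SCR. It does not: that titer defines each subject's seroconversion status. This is also a plausible reason for treating the endpoints differently, since a Day 28 GMT carries no baseline information unless it is modelled. Only adjustment of the between-arm comparison is missing.
- A reader might infer that chance baseline imbalance leaves the SCR decision unprotected. Under randomisation the interval's width allows for it, as the 2.6% error rate shows. Stratification by site, age and 2018-19 vaccination may reduce it further.
- A reader might infer that the trial is underpowered, or that adjustment brings a known large gain. The 90% target is met, and the gain rests on inputs the documents do not contain.

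There is also a fair objection of proportion: changing a primary decision rule is more than a coding detail, and the adjusted difference could instead be a sensitivity analysis. That is the lighter course, but a sensitivity analysis leaves the power of the primary decision unchanged.

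**Conclusion.** This is a cheap, optional gain in precision. The SCR difference alone limits overall power and is compared without adjustment for the Day 0 titer, while the GMT ratio, which has power to spare, is adjusted.

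For assumed R2 of about 0.02–0.17 and independent strains, four-strain power goes from about 90% to about 91–96%. At R2 = 0.10 the risk of missing a true result falls from 9.8% to 5.9%, about two fifths. The gain is smaller if strain results are correlated, and could be negligible if the Day 0 titer predicts seroconversion poorly. Type I error is essentially unchanged. The direction is sound; the size depends on data that only the sponsor holds.

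**What to change.** First estimate, strain by strain, the R2 of seroconversion on Day 0 titer in the qNIV-E-201 data. If it is worthwhile, amend SAP 7.1.1, SAP 12.2 and Protocol 10.4.1.1 before the Day 28 unblinding as follows.
- The primary SCR interval for each strain becomes a standardised (marginal) risk difference over the per-protocol set. The model terms are treatment, log10 Day 0 titer and an indicator for Day 0 below 10, with a robust standard error.
- The -10% margin and the requirement that all eight comparisons succeed are unchanged.
- The crude Newcombe interval is reported beside it as supportive.

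The cost is an amendment to both documents and a short, validated macro. The real downside is that the primary interval becomes model-based and has to be explained to the agency. No extra subjects, samples or assays are needed.
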